Date: 4.14.2023

Principal Investigator: [name].

Application Number: IRB000182576

Title: Cortical functional connectivity as an early biomarker of recovery in spinal cord injury

Number: IRB00182576

Principal Investigator: [name]

NCT Number: NCT03854214

Approval Date: 11/29/2018

Document Date: 4/14/2023

JHM IRB - eForm A – Protocol

- Use the section headings to write the JHM IRB eForm A, inserting the appropriate material in each. If a section is not applicable, leave heading in and insert N/A.
- When submitting JHM IRB eForm A (new or revised), enter the date submitted to the field at the top of JHM IRB eForm A.

1. Abstract

- a. Provide no more than a one page research abstract briefly stating the problem, the research hypothesis, and the importance of the research.

Early detection of response to therapeutic intervention in patients with chronic spinal cord injury (SCI) is crucial, as it will enable early adjustment or termination of intervention in non-responding patients, minimizing undue stress and financial burden. The goal of this study is to establish resting state fMRI (rsfMRI) outcome measures as novel non-invasive imaging biomarkers for early prediction of neurological improvements in response to intervention.

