Functional electrical stimulation (FES) cycling is an intervention for SCI patients, in which patterned electrical pulses are delivered to lower extremity muscles to initiate cycling movement. Our group has shown that FES cycling, but not passive cycling (i.e., movement is driven only by the cycle's motor, without electric stimulation), leads to improvements in sensorimotor function, as measured using the International Standard of Neurological Classification for Spinal Cord Injury (ISNCSCI) scoring system. Unfortunately, early detection of response to intervention using ISNCSCI alone is challenging, as observation of clinically significant improvement (increase in ISNCSCI scores) requires at least 4 weeks of intervention. In contrast, previous tfMRI studies have shown that cortical reorganization can be observed after as little as one week of intervention. We hypothesize that reorganization of the sensorimotor cortex underlies neurological and functional recovery during intervention, and that such cortical reorganization will occur prior to observation of clinical improvement. We therefore propose that rsfMRI outcome measures, such as between-network connectivity (BNC; calculated as the degree of temporal dependency between functional networks), can be used to detect early changes in brain functional networks that are predictive of recovery.

Date: 4.14.2023

Principal Investigator: [name].

Application Number: IRB000182576

If successful, these studies will: 1) provide a new and effective clinical tool to study plastic cortical changes that occur after SCI, 2) provide new imaging biomarkers that are predictive of progress towards recovery in response to therapy, and 3) extend our knowledge about the functional reorganization that takes place during and after therapeutic intervention. The developed methods may have broader applications in number of other diseases that affect motor functions, such as stroke and Parkinson's disease.

2. Objectives (include all primary and secondary objectives)

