Aim 1. Characterize the baseline time profile of the rsfMRI outcome measures in chronic SCI patients, acquired over 4 weeks of passive (sham) cycling. In order to quantitatively assess the sensitivity of rsfMRI outcome measures to early functional reorganization that occurs in response to FES cycling, baseline time profile of the outcome measures in the absence of the active stimulation must be established. Accordingly, patients will participate in a 4-week passive cycling program. At weeks 0, 2, and 4, sensory and motor network BNC (calculated using ICA- and SCA-derived brain parcels) and ISNCSCI scores will be measured. *Hypothesis: we will observe stable baseline measures of sensory and motor cortex BNC and ISNCSCI scores of the patients during the 4-week passive cycling program, with minimal to no change in values.*

Aim 2. Characterize the time profile of the cortical reorganization in chronic SCI patients that occurs during a 4-week FES cycling program. *Hypothesis: We will observe early sensorimotor cortex BNC changes after 2 weeks of FES cycling, that are predictive of changes in ISNCSCI scores at week 4.* Specifically, we hypothesize that: a) Changes in sensory network BNC at week 2 will correlate with changes in sensory ISNCSCI scores at week 4; b) Changes in motor network BNC at week 2 will correlate with changes in motor ISNCSCI scores at week 4. To test these hypotheses, we will first measure the sensory and motor network BNC and ISNCSCI scores at weeks 0, 2, and 4, then correlate the changes in sensory and motor network BNC at week 2 with the changes in respective ISNCSCI scores at week 4. Finally, longitudinal (pre- and post- intervention) inter- and intra-subject reproducibility of the ICA- and SCA-derived parcels will be assessed.

3. Background (briefly describe pre-clinical and clinical data, current experience with procedures, drug or device, and any other relevant information to justify the research)

Spinal Cord Injury and Rehabilitation.

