development of a robust, clinically feasible rsfMRI data analysis pipeline, this study is expected to result in improved understanding of the functional reorganization that takes place during and after intervention.

4. Study Procedures

- Study design, including the sequence and timing of study procedures (distinguish research procedures from those that are part of routine care).

This will be an early phase 1 (phase 0) clinical trial. Specifically, the study will be performed as a randomized, parallel group trial to determine if the amount of changes in brain functional connectivity outcome measures (i.e., between network connectivity) is significantly different between the group of patients that perform FES cycling and another group of patients that perform passive (sham) cycling.

Patients of the International Center for Spinal Cord Injury (ICSCI) at the Kennedy Krieger Institute (KKI) will be identified as meeting the inclusion criteria by reviewing the medical records held by the ICSCI. Once the patient consents by signing the consent form, official screening of subjects will be performed. Subjects will be randomized into 2 groups: FES cycling (Group 1; n=24) and passive cycling (Group 2; n=24). The patients will undergo either an FES cycling or a passive cycling sessions for 4 weeks, 3 times a week. **Acquisition of rsfMRI measures:** MRI will be performed on all participants at the beginning (prior to cycling sessions) and at the end of the 2nd and 4th weeks of the intervention program. **Acquisition of clinical measures:** ISNCSCI and SCIM (Spinal Cord Independence Measure) evaluations will be performed to coincide with the dates of MRI acquisitions, to determine the neurological level and the degree of sensory and motor impairments. Detailed study timeline can be found in Figure 1.

[figure not shown]

Figure 1. Study Timeline.

- SCI patients assigned to FES cycling group will take part in the following evaluations:
 - Medical chart review / MRI screening questionnaire
 - FES cycling trial
 - Neurological evaluation (ISNCSCI – more commonly known as ASIA exam)
 - Functional evaluation (SCIM)
 - MRI

Date: 4.14.2023

Principal Investigator: [name].

Application Number: IRB000182576

E1: FES cycling

- SCI patients assigned to passive cycling group will take part in the following evaluations:
 - A: Medical chart review / MRI screening questionnaire
 - B2: Passive cycling trial

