Preliminary study: In this preliminary study, we hypothesized that BNC of sensorimotor and visual networks will correlate with the total ISNCSCI score, and performed the study to determine the feasibility of a larger population study. Twelve SCI patients were recruited, and the relationship between the ISNCSCI score and BNC measurements was examined. ISNCSCI sub-scores were first obtained, which were: total upper and lower body motor scores, and total sensory score. The sum of the three scores provided the total ISNCSCI scores. Analysis of the data consisted of preprocessing, PCA, and GICA, and total of 14 intrinsic functional components were identified. BNC between the sensorimotor and visual networks were computed, and plotted against the total ISNCSCI scores. Linear regression analysis was performed to find the best linear fit for the plots. Stronger BNC between the sensorimotor and visual networks was associated with lower total ISNCSCI scores ($R^2=0.35$, $p = 0.04$; [Figure 2](#)[Figure 2](#)). In other words, patients with greater degree of physical impairment tended to have stronger functional connectivity between the sensorimotor and visual networks, suggesting compensatory plastic cortical changes that are related to clinical presentation of the patients. Overall, BNC measures showed good correlations with the total ISNCSCI scores, supporting our hypothesis.

Between network connectivity (BNC) measurements from the above preliminary study provided means, standard deviations, and correlation coefficients for 12 SCI patients. A power analysis¹ revealed that a sample size of 24 subjects will be required to achieve 80% power at an alpha of 0.018; the alpha level was lowered with the correction for multiple comparisons in mind. We will therefore recruit a total of 48 patients. At this point, we do not have enough information about the variability of the BNC in response to the FES to perform a more stringent power analysis. We will use the data in the first 24 SCI subjects recruited to the study to assess the degree of variability in the metric. Based upon these estimates, we will then perform a power analysis to determine how many more subjects will need to be enrolled to assess the significance of our findings.

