The spatial maps of ICA- and SCA-derived brain parcels will be compared across groups. First, the participant-specific sensory and motor brain parcels will be converted to z values, so image intensities reflect the degree to which the parcel is present in each participant's data. The brain parcels will be combined in a second-level random effects analysis using a two sample t-test in SPM8. Voxels that contributed unequally to the parcels across groups will be identified using a liberal voxel-wise p value of 0.01 and a cluster-level p value of 0.05 corrected for multiple comparisons². The between network connectivity (BNC) between sensory and motor parcels will be calculated using Pearson's correlation coefficient between pairs of participant specific motor and sensory brain parcels³. Pairwise-correlations will be converted to Z-scores using Fisher's transformation, and the BNC across groups will be compared using two-sample t tests and adjusted p-values using a false discovery rate correction. Next, we will investigate whether sensory and motor BNC measured at week 2 of cycling program are related to motor and sensory International Standards for Neurological Classification of Spinal Cord Injury (ISNCSCI) scores measured at week 4, using a multivariate linear regression model analysis. Finally, the longitudinal inter- and intra-subject reproducibility of the ICA- and SCA-derived brain parcels will be assessed using intra-class correlation coefficient (ICC).

d. Early stopping rules.

[figure not shown]

Figure 2. Correlations between sensorimotor-visual BNC measurements and total ISNCSCI scores in SCI patients suggest a compensatory plastic cortical changes that are related to clinical presentation of the patients. Patients with lower ISNCSCI score showed larger degree of functional connectivity between the sensorimotor and visual networks.

Date: 4.14.2023

Principal Investigator: [name].

Application Number: IRB000182576

The principal investigator may discontinue the study if the interim statistical analysis as described above indicates that the number of subjects required for this trial exceeds 50.

Patients may withdraw from the study at any time for any reason. Any investigator may discontinue a patient for any of the following reasons:

- The subject experiences a medical emergency that necessitates discontinuation of therapy

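### The stated goal is early prediction of individual improvement, but the planned correlation and regression show only in-sample association; nothing measures prediction error in a new patient

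*Combined protocol and SAP*

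**What the plan says.** The Abstract sets the goal as establishing "novel non-invasive imaging biomarkers for early prediction of neurological improvements in response to intervention" and motivates it by saying that "it will enable early adjustment or termination of intervention in non-responding patients". It then proposes that measures such as BNC "can be used to detect early changes in brain functional networks that are predictive of recovery".

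Aim 2 (Section 2) hypothesises BNC changes at week 2 of FES cycling "that are predictive of changes in ISNCSCI scores at week 4". Its test is to "correlate the changes in sensory and motor network BNC at week 2 with the changes in respective ISNCSCI scores at week 4", with sensory BNC matched to sensory scores and motor BNC to motor scores.

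Section 7c asks whether week-2 BNC is related to ISNCSCI "scores measured at week 4, using a multivariate linear regression model analysis". It gives no analysis set, list of predictors, measure of predictive accuracy, reference model or validation step. The false discovery rate correction there is stated for the between-group BNC t tests, and the intra-class correlation concerns reproducibility of the parcels. Section 9 makes later use of the measures conditional on their being validated, but this study plans no validation.

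**The concern.** A fitted correlation or regression answers whether two quantities move together in the patients studied. A biomarker for individual prediction has to answer how far the forecast would be from the outcome in a patient who did not help to fit the model. The plan contains the first and claims the second.

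The gap widens with model size, and the plan does not fix model size. There are two parcellations (ICA and SCA). Section 7a offers BNC as one example of a connectivity measure and adds its mean, variance and dynamic properties. Section 7b lists covariates that may enter the analysis. In-sample R-squared rises with every term, whether or not the term carries information.

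Aim 2 correlates changes, whereas Section 7c regresses week-4 scores on week-2 BNC. The pilot in Section 7c found BNC related to severity at a single time point. A fit of level on level could therefore reflect stable severity and say little about response to cycling.

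At stake is the label on the result: a real but modest association, or an overfitted one, could be reported as early prediction of recovery.

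**Working it through.** **Inputs.** FES arm n = 24 (Section 4a; Aim 2 concerns FES cycling). Both arms pooled, n = 48. Pilot: 12 patients, R² = 0.35, p = 0.04 (Section 7c). Optional covariates (Section 7b): age, sex, handedness, time since injury, stimulation strength, stimulation frequency and session duration, seven in all. The number of BNC terms is not stated, so one and two are assumed, and nine for two BNC terms plus all seven covariates.

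**The plan's own figure.** Section 7c says "a sample size of 24 subjects will be required to achieve 80% power at an alpha of 0.018". It names neither the effect size nor the test; the pilot correlation |r| = √0.35 = 0.592 is assumed. The pilot p-value recomputes to 0.043. For the sample size, two-sided Fisher z gives

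n = ((2.366 + 0.842) / atanh(0.592))² + 3 ≈ 25.2, so 26.

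Other versions give 22 (one-sided Fisher z), 23 (one-predictor F test) and 25 (simulated correlation test, with 78.9% power at 24). All are within two of 24, so the figure reproduces as the size needed to detect a correlation. It says nothing about prediction accuracy.

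**Chance fit.** With no true relation and p predictors, R² follows Beta(p/2, (n − p − 1)/2), with mean p/(n − 1).

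| Terms | Mean R², n = 24 | 95th percentile, n = 24 | P(R² ≥ 0.35), n = 24 | Mean R², n = 48 |
|---|---|---|---|---|
| 1 | 1/23 = 0.04 | 0.16 | 0.2% | 1/47 = 0.02 |
| 2 | 2/23 = 0.09 | 0.25 | 1.1% | 2/47 = 0.04 |
| 9 | 9/23 = 0.39 | 0.63 | 60% | 9/47 = 0.19 |

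**Leave-one-out at n = 24** (simulated, independent normal predictors). The simulation gave R² against the full-sample mean. The fair reference also leaves the patient out, and its error is 24/23 times larger, so R²cv = 1 − (1 − R²) × (23/24)², with (23/24)² = 0.918.

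| Truth | Terms | In-sample mean | Leave-one-out, full-sample mean | Leave-one-out, fair reference |
|---|---|---|---|---|
| No relation | 1 | 0.04 | −0.14 | −0.05 |
| No relation | 2 | 0.09 | −0.20 | −0.11 |
| No relation | 9 | 0.39 | −0.90 | −0.74 |
| R² = 0.35 | 1 | 0.36 | 0.24 | 0.30 |
| R² = 0.35 | 2 | 0.39 | 0.19 | 0.26 |
| R² = 0.35 | 9 | 0.59 | −0.28 | −0.18 |

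Real signal survives the check in a small model. In the nine-term model a true R² of 0.35 appears as 0.59 in sample, while the model predicts worse than the mean.

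**Significance is not accuracy.** With one predictor at n = 24, p < 0.018 needs |r| ≥ 0.479, so R² ≥ 0.23. The residual SD is then √(1 − 0.23) = 0.88 of the raw SD, a 12% reduction. At R² = 0.35 it is √0.65 = 0.81, a 19% reduction.

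**Is beating the reference enough?** Under no relation at n = 24, leave-one-out error is below that of the mean-only model in about 18% of trials with one predictor and about 15% to 16% with two. The planned alpha is 1.8%.

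**Several looks.** Treating sensory and motor BNC under ICA and SCA as four independent tests, the chance of at least one false positive is 1 − 0.982⁴ = 7.0% at 0.018.

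**The case against.** A reader might infer that chance fit in about 24 patients will be reported as prediction, for example that a worthless model would show the pilot's R² of 0.35 and pass. The documents do not support that. Section 7c asks only whether BNC is related to the scores, and it does not say that the model will be judged on R² alone. For a pre-specified model the overall F test keeps its size: in simulation at n = 24 with no relation it rejected at 0.05 in 5.0%, 4.8% and 5.1% of runs for 2, 4 and 8 predictors, and in about 2% at 0.018. A mean null R² near 0.35 needs about eight predictors (8/23), a number the plan does not state. With one or two terms, a null R² of 0.35 or more occurs in roughly 0.2% to 1.2% of trials. Chance fit would pass as prediction mainly if R² were read without its p-value, or if network pairs, parcellations or covariates were selected on the data.

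A reader might also infer that therapy will be changed in this trial on the basis of BNC. It will not: that sentence in the Abstract is motivation, the study is early phase 1, and Section 9 defers use until after validation. Nor is the regression the only relevant analysis. Aim 2 adds a correlation, although it too is in-sample, and the between-group BNC comparison answers a different question.

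These points limit the size of the problem. They do not supply a measure of error in a new patient, and the goal and Aim 2 still speak of prediction.

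**Conclusion.** The point holds as a mismatch between claim and evidence. The planned correlation and regression can establish an association between early BNC and week-4 ISNCSCI. They cannot show how well BNC predicts an individual's outcome, or whether it adds to what baseline ISNCSCI already tells.

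The optimism is small if one or two BNC terms are fixed in advance (null mean R² 0.04 to 0.09) and large if all seven optional covariates join two BNC terms (0.39). It is about half as large if both arms are pooled. These figures rest on assumed predictor counts, on independent normal predictors in the simulations, and on reading Aim 2 as an FES-arm analysis with no losses. Section 7c does not name the analysis set. Compliance removals under Section 4f could bring n below 24.

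This should be changed because the remedy is cheap and more informative than the stated analysis. It does not invalidate the planned association test.

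**What to change.** In Section 7c, keep the planned association test at its stated alpha and add the following.

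- **Accuracy.** Leave-one-out or repeated k-fold prediction of week-4 ISNCSCI change in the FES arm. Any choice of network pair, parcellation or covariate is made inside each fold.
- **Reporting.** Cross-validated R² and mean absolute error in ISNCSCI points, with an interval, against a model without BNC that uses baseline ISNCSCI only and is run through the same folds.
- **Wording rule.** Use the word *predictive* only if the association test, adjusted for the BNC measures tried, is significant and the cross-validated error is lower than the reference. Because both conditions are required, the false-positive rate cannot exceed that of the adjusted test. Otherwise report an association that needs later validation.

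The cost is a paragraph of SAP text and a few lines of code, with no new patients, scans or visits. The downside is that reported accuracy will look less favourable and will be imprecise: at n = 24 with one predictor and a true R² of 0.35, the 95% range of leave-one-out R² is about −0.03 to 0.62.

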The risks associated with functional evaluation (SCIM) are extremely low. The tasks could cause boredom or maybe distracting for some participants. **To minimize the risk**, study participants will be informed that they are free to take breaks while answering the questionnaire as often as necessary.

D: MRI

The risks associated with magnetic resonance imaging are extremely low. They include the possibility that undetected metal in the subject's body could be displaced by the magnetic field of the MRI scanner.

Participants could become claustrophobic while in the scanner. Participants could experience discomfort in attempting to remain still for up to 90 minutes in the scanner. The tasks could cause boredom or anxiety in some participants. Credit cards, watches, or other items could be damaged by the magnetic field if they are inadvertently brought into the scan room. Some volunteers may experience dizziness when being in the scanner. Head phones and ear-plugs are provided to the subjects to protect subjects from scanner gradient noise. **To minimize risk**, following measures will be taken:

- All subjects are screened for contra-indications for magnetic resonance, namely severe claustrophobia, pregnancy, cardiac pacemaker, orthodontics (braces) or other non-MR compatible ferromagnetic implant. In addition, access to the scan room is strictly controlled to ensure that no ferromagnetic materials are introduced. The scanners to be used in these studies are FDA approved and operates under radiofrequency power monitoring software at all times. All scan procedures at magnetic field strengths of 3T are FDA approved and are not classified as investigational devices.
- The subjects have the option of terminating the testing at any time without penalty if they so choose. The risks of psychological discomfort will be minimized by encouraging subjects to let the examiner know if they are feeling any discomfort, and by continuous monitoring by experienced operators for subject fatigue, inattention, or annoyance. Scanning will be halted if the subject so requests, or if the examiner feels that the subject is becoming uncomfortable. The subject will be encouraged to report any adverse symptoms during the MRI. The MRI can be stopped by the subject either by verbalizing the request to stop (which can be heard through the microphone in the MRI) or by pushing a “panic button” provided.
- A potential concern with MRI studies is so-called radiofrequency heating due to radiofrequency power deposition in the subject. The FDA has set strict and very conservative guidelines to guard against this risk. Such power deposition increases with the square of the magnetic field strength. However, it is possible to stay within these guidelines. To be 100% sure of compliance with the FDA guidelines, power deposition is monitored continuously by the software of the manufacturers and scans are not possible if the power deposition would exceed guidelines.
- This study includes operator-controlled changes to the pattern and timing of an MRI signal or pulse sequence that varies from the standard sequences used by the MRI manufacturer at lower field strengths. These changes will operate within FDA guidelines.

Other risks: Time commitment

The time commitment required to complete all study over 4 weeks may be inconvenient. **To minimize this risk**, the participant: 1) will be instructed to contact the study coordinator if the participant is having problems scheduling study visits, or adhering to scheduled study visits ahead of time; 2) will be excluded from the study if the participant cannot commit the time and effort to the study; 3) will be told that the start of the study will be arranged in such a way that it reduces any disruption to the participant's social, work or school commitments.

c. Plan for reporting unanticipated problems or study deviations.

During this study, medical history and physical examination will be performed at baseline and at regular intervals for measurement of residual sensorimotor functions in patients with spinal cord injury. All of the materials collected are for research purposes only, and data will be kept in strict confidence. No information will be given to anyone without permission from the subject. The consent form includes the informed consent statement required by Johns Hopkins University School of Medicine for studies involving human subjects. This statement guarantees confidentiality, which will be ensured by use of identification codes. All data, whether generated in the laboratory or at the bedside, will be identified with a randomly generated identification code unique to the subject.

The Principal Investigator (PI) will be responsible for ensuring participants' safety on a daily basis. The PI will also monitor participant safety, evaluate the progress of the study, to review procedures for maintaining the confidentiality of data, the quality of data collection, management, and analyses. [name], M.D., is the Clinical Director of the International Center for Spinal Cord Injury (ICSCI), and she will aid the PI in her capacity as a clinical mentor of the study in monitoring the study's participants' safety.

Adverse events (AE), unanticipated problems and/or study deviations will be reported in writing by the PI to the Johns Hopkins Medical Institute-IRB and Kennedy Krieger Institute Office of Research Compliance within 24 hours of notification. AE reports and annual summaries will not include subject- or group-identifiable material. Each report will only include the identification code. Twice annually, the PI will review study progress, data quality, and participants safety and share the reports with other study members of the group.

All research material will be kept confidential and any means of subject identification (name and history number) will be removed from all material for analysis or presentation. No identifying information will be made publicly available. In some cases, individual scans will be included in published papers or meeting papers or posters, but the identity of the subject in question will not be revealed. There are minimal legal risks associated with breach of confidentiality for this study. To minimize the risk of breach of confidentiality, access to participant/study data will be limited to study team members only. All study data will be stored in a departmental locked cabinet and secure database program.

d. Legal risks such as the risks that would be associated with breach of confidentiality.

There are minimal legal risks associated with breach of confidentiality for this study. To minimize the risk of breach of confidentiality, access to participant/study data will be limited to study team members only. All study data will be stored in a departmental locked cabinet and secure database program. Additionally, all research material will be kept confidential and any means of subject identification (name and history number) will be removed from all material for analysis or presentation. No identifying information will be made publicly available. In some cases, individual scans will be included in published papers or meeting papers or posters, but the identity of the subject in question will not be revealed.

e. Financial risks to the participants.

There are no financial risks to participants for any of the study tests. There will be no cost to the participant or the participant's insurance company for the MRI scans done specifically for this study. The scans will be paid by funds from this grant application. Subjects will be responsible for the cost of travel to and from the Institute, as well as any food/meals purchased throughout the day while engaged in study procedures. Valet parking is available at no cost.

Date: 4.14.2023

Principal Investigator: [name].

Application Number: JRB000182576

9. Benefits

- a. Description of the probable benefits for the participant and for society.

Individual subject: There is no direct benefit to the individual subject, except that the MRI report they receive may contain information useful to their physicians.

Society: Once developed and validated, the proposed MRI measures may yield surrogate biomarkers of treatment and/or rehabilitation therapy responses in SCI patients for use in clinical trials and drug discovery. Additionally, the developed methods may have broader implications in a number of other movement disorders (e.g., stroke and Parkinson's disease).

10. Payment and Remuneration

- a. Detail compensation for participants including possible total compensation, proposed bonus, and any proposed reductions or penalties for not completing the protocol.

After completing the study, participants will receive a total of \$525 compensation for their contribution. The costs for each visit are as follows:

- MRI visits: 3 sessions at \$25 per session, totaling \$75.
- ASIA visits: 3 sessions at \$50 per session, totaling \$150.
- FES visits: 12 sessions at \$25 per session, totaling \$300.

Compensation will be provided via a check, and participants will receive a structural images of their brain as a souvenir.

11. Costs

- a. Detail costs of study procedure(s) or drug (s) or substance(s) to participants and identify who will pay for them.

There is no cost to study participants for any of the study tests. Subjects will be responsible for the cost of travel to and from the Kennedy Krieger Institute (Valet parking is available at no cost to study participant), as well as any food/meals purchased throughout the day while engaged in study procedures.
